7.2 Criteria for evaluation

All subjects who complete day 1, 28, 44 and 72 assessments (including all euglycaemic clamps) will form part of the evaluable cohort.

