4.3 Withdrawal of Subjects and Discontinuation Criteria

Subjects have the right to withdraw from the study at any time for any reason. The investigator also has the right to withdraw subjects from the study in the event of intercurrent illness, adverse events, protocol violations, administrative reasons or other reasons. An excessive rate of withdrawals can render the study impossible to interpret. Therefore, unnecessary withdrawal of subjects should be avoided. Should a subject decide to withdraw, all efforts will be made to complete and report the observations as thoroughly as possible.

The investigator should contact the subject either by telephone or through a personal visit or a responsible relative must be contacted to determine as completely as possible the reason for the withdrawal. A complete final evaluation at the time of the patient's withdrawal should be made with an explanation of why the subject is withdrawing from the study. If the reason for removal of a subject from the study is an adverse event or an abnormal laboratory test result, the principal specific event or test will be recorded on the Case Report Form.

A subject will be considered to have withdrawn from the study if they do not complete all euglycaemic clamp procedures (day 1, 28 and day 72).

Subjects may be replaced at the discretion of the investigator.

5. Treatment of subjects

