The following study assessments will be performed (subjects will have fasted for at least eight hours):

- Adverse events
- Concomitant medication
- Vital signs (during the clamp procedure vital signs will occur every 30 minutes)
- Height/ weight/ BMI
- Measurement of waist and hip size

- Haematology: complete blood count (FBC) with differential and platelet count (haemoglobin, haematocrit, erythrocyte count, white blood count, differential white blood cell count, platelets)
- Biochemistry safety labs assessment for standard clinical chemistry (fasting glucose, creatinine, sodium, potassium, calcium, aspartate aminotransferase, alanine aminotransferase, bilirubin), including thyroid hormones (TSH, ft4), lipids (triglycerides, cholesterol, cholesterol HDL & LDL Sub-fractions) CRP and HbA1c
- Urinary analysis (pH, specific gravity, leucocytes, nitrite, protein, glucose, ketones, urobilinogen, bilirubin, erythrocytes) and urine drug screen
- Pregnancy testing and LMP date in WOCBP subjects
- Adiponectin, leptin, ghrelin, testosterone
- Pituitary hormone function tests
- Dietary Questionnaire
- Sleep Questionnaires (PSQI)
- Euglycaemic clamp 2
- Insulin will be titrated 3 times during euglycaemic clamp procedure according to approved and verified formula sheet.
- ECG monitoring at 30 minute intervals during the clamp procedure
- Indirect calorimetry (Group 1)

Day 29 - Day 43

Wash out Period

Day 44

Subjects will be admitted to the unit in the morning and remain on the unit for approximately one to two hours. Subjects randomized to Group 2 will take their first dose of study medication in the unit in the morning of the visit.

The following study assessments will be performed (subjects must have fasted for at least 8 hours):

- Adverse events
- Concomitant medication
- Vital signs: temperature, blood pressure, heart rate, respiration rate, oxygen saturation
- Height/ weight/ BMI

- Measurement of waist and hip size
- Haematology: complete blood count (FBC) with differential and platelet count (haemoglobin, haematocrit, erythrocyte count, white blood count, differential white blood cell count, platelets)
- Biochemistry safety labs assessment for standard clinical chemistry (fasting glucose, creatinine, sodium, potassium, calcium, aspartate aminotransferase, alanine aminotransferase, bilirubin), including thyroid hormones (TSH, ft4), lipids (triglycerides, cholesterol, cholesterol HDL & LDL Sub-fractions) CRP and HbA1c

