- Urinary analysis (pH, specific gravity, leucocytes, nitrite, protein, glucose, ketones, urobilinogen, bilirubin, erythrocytes) and urine drug screen
- Pregnancy testing and LMP date in WOCBP subjects
- Adiponectin, leptin, ghrelin, testosterone
- Pituitary hormone function tests
- Dietary Questionnaire
- Sleep Questionnaires (PSQI)

Day 72

Subjects will be admitted to the unit in the morning and remain on the unit for approximately four to six hours. Subjects will take their last dose of study medication (Group 2) in the unit in the morning of the visit.

The following study assessments will be performed (subjects must have fasted for at least 8 hours):

- Adverse events
- Concomitant medication
- Height/ weight/ BMI
- Vital signs (during the clamp procedure vital signs will occur every 30 minutes)
- Measurement of waist and hip size
- Haematology: complete blood count (FBC) with differential and platelet count (haemoglobin, haematocrit, erythrocyte count, white blood count, differential white blood cell count, platelets)
- Biochemistry safety labs assessment for standard clinical chemistry (fasting glucose, creatinine, sodium, potassium, calcium, aspartate aminotransferase, alanine aminotransferase, bilirubin), including thyroid hormones (TSH, ft4), lipids (triglycerides, cholesterol, cholesterol HDL & LDL Sub-fractions) CRP and Hb1aC

- Urinary analysis (pH, specific gravity, leucocytes, nitrite, protein, glucose, ketones, urobilinogen, bilirubin, erythrocytes) and urine drug screen
- Pregnancy testing and LMP date in WOCBP subjects
- Adiponectin, leptin, ghrelin, testosteron
- Pituitary hormone function tests
- Dietary Questionnaire
- Sleep Questionnaires (PSQI)
- Euglycaemic clamp 3
- Insulin will be titrated 3 times during euglycaemic clamp procedure according to approved and verified formula sheet.
- ECG monitoring at 30 minute intervals during the clamp procedure
- Indirect calorimetry (Group 2)

Follow up (Day 100)

The subject will be contacted by telephone approximately 28 days after the final euglycaemic clamp day to check whether they have experienced any adverse events. This follow up phone call should be documented in the subject's notes. WOCBP should take a home pregnancy test.

Early termination visit

If a subject withdraws or is discontinued from the study the subject should attend if at all possible for a discontinuation visit and undergo the following procedures:

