6.1 Euglycaemic Clamp

Following completion of the procedures mentioned above on days 1, 28 and 72 a euglycaemic clamp study will be performed to determine the extent of total and non-oxidative glucose disposal. After an overnight fast of at least 8 hours, the subject will be admitted to the Clinical Research Facility. This procedure will take approximately 3 hours. A primed/ continuous intravenous infusion of insulin, through an intravenous cannula, will commence in the morning at

an infusion rate dictated by the verified formula sheet, maintaining a mid-physiological level of hyperinsulinaemia for 180 minutes. Whole blood glucose will be assayed from a separate intraveneous cannula every 5 minutes. A negative feedback formula will be used to adjust the rate of infusion of 20 % dextrose in order to maintain euglycaemia at 4.5 mmol.L⁻¹. Whole blood potassium and haematocrit is measured at 30 minute intervals during the clamp procedure with electrocardiographic monitoring half hourly in order to monitor for changes towards hypokalaemia.

At 180 min, the insulin and glucose infusion is stopped immediately, and the subject fed. A final blood sugar, potassium and haematocrit level, and vital signs check will be performed before the subject is discharged from the unit.

The visit window for the euglycaemic clamp is up to plus or minus two days. All other visits should be adjusted accordingly.

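### Section 7.2 makes the clamp-free Day 44 visit a condition of the only non-safety analysis cohort, so a subject with all three clamps could be left out of the primary analysis, whose set 7.3 does not name

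*Combined protocol and SAP*

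**What the plan says.** Section 7.2 defines one cohort: "All subjects who complete day 1, 28, 44 and 72 assessments (including all euglycaemic clamps) will form part of the evaluable cohort". The only other sets are safety sets (opening of section 7, 7.3 and the safety subsection 7.3.1). Section 7.3 gives the primary crossover model and the 90% confidence interval rule but does not say which subjects the model is fitted to.

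The clamp schedule is in 6.1: "Following completion of the procedures mentioned above on days 1, 28 and 72 a euglycaemic clamp study will be performed". Sections 3.2 and 4.3 and Appendix 1 agree on those three days. The Day 44 entry in section 6 describes a short visit: "Subjects will be admitted to the unit in the morning and remain on the unit for approximately one to two hours". It covers vital signs, body measurements, laboratory tests and questionnaires such as "Sleep Questionnaires (PSQI", and no clamp. It also starts dosing in one sequence: "Subjects randomized to Group 2 will take their first dose of study medication in the unit in the morning of the visit".

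Section 4.3 applies a different completion test. A subject counts as withdrawn "if they do not complete all euglycaemic clamp procedures (day 1, 28 and day 72", and Day 44 is not mentioned. The same section lets the investigator withdraw a subject "in the event of intercurrent illness, adverse events, protocol violations, administrative reasons or other reasons", and adds: "Subjects may be replaced at the discretion of the investigator".

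**The concern.** Sections 4.3 and 7.2 disagree about who has completed. A subject with clamps on Days 1, 28 and 72 and an incomplete Day 44 is not withdrawn on the 4.3 clamp test, yet does not meet 7.2.

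Either reading of 7.2 leaves a problem. If its cohort is the primary set, complete primary data can be discarded in a trial of 16 that has no dropout allowance. If it is not, the primary set is unnamed in an open comparison with no treatment, and could be settled after the results are seen.

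**Working it through.** **Does the primary analysis need Day 44?** The endpoint is change in clamp-measured glucose disposal (3.1), and there is no Day 44 clamp. The primary model in 7.3 has treatment, period, sequence and subject. The covariates named, for exploratory analyses, are age, baseline BMI, sex and race. No Day 44 measurement is named, although 7.3 allows ANCOVA for confounders that it does not list.

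**Inputs.** SD of difference 1.4 and margin ±1.1 (7.1); eight per sequence (4.1, 7.1); 90% interval, so two one-sided 5% tests (7.3; 7.1 states no alpha).

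**Assumptions.** The SD, which 7.1 gives for baseline to week 4, also applies to the within-subject dolutegravir minus no-treatment contrast. True difference 0. Excluded subjects are not replaced.

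**Formulas.** SE = (1.4/2) × √(1/n1 + 1/n2). Half-width of the 90% interval at that SD = t(0.95, df) × SE. Power is the probability that the interval lies within ±1.1, integrated over the chi-square distribution of the variance estimate. The degrees of freedom are n-2 for the two-period contrast, or 2n-3 if all three clamps are modelled (3n observations less n subject, 2 visit and 1 treatment terms).

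**The plan's own figure.** With 8/8, SE = 0.7 × √(1/8 + 1/8) = 0.350, half-width = 1.761 × 0.350 = 0.616, and power is 82.0% on 14 df. That agrees with the stated 80%. On n-2 df, 16 is the smallest total that reaches 80%.

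**Effect of exclusions.**

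| Subjects per sequence | SE | Half-width (n-2 df) | Power, n-2 df | Power, 2n-3 df |
|---|---|---|---|---|
| 8/8 | 0.3500 | 0.616 | 82.0% | 84.5% |
| 7/8 | 0.3623 | 0.642 | 78.1% | 81.1% |
| 7/7 | 0.3742 | 0.667 | 73.9% | 77.5% |
| 6/8 | 0.3780 | 0.674 | 72.7% | 76.4% |

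The first exclusion costs 82.0 - 78.1 = 3.9 points on n-2 df, or 84.5 - 81.1 = 3.4 points on 2n-3.

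**Sensitivity (n-2 df, 8/8 to 7/8).** SD 1.2: 93.4% to 91.2%. SD 1.6: 66.7% to 61.6%. SD 1.4 with true difference 0.2: 75.8% to 72.0%.

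**How often.** The documents give no rate of incomplete Day 44 visits, so the per-subject rates p below are assumptions. The chance of at least one exclusion is 1 - (1-p)^8 if only Group 1 is affected and 1 - (1-p)^16 if both groups are. Expected power is the binomial average on n-2 df.

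| p | Group 1 only: chance; expected power | Both groups: chance; expected power |
|---|---|---|
| 2% | 15%; 81.4% | 28%; 80.7% |
| 5% | 34%; 80.3% | 56%; 78.6% |
| 10% | 57%; 78.4% | 81%; 74.7% |

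**The case against.** **The exclusion is not stated.** Section 7.2 says who is in the cohort. It does not say that anyone else is barred from an analysis, and no section assigns the cohort to the primary model. This stands: a reader might infer that the plan definitely drops these subjects, and the documents do not go that far. But the section is headed as criteria for evaluation and no other non-safety set exists. If the criteria do not restrict the primary analysis, its set is undefined.

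**Day 44 matters to the trial.** It is tempting to call the visit unrelated to the endpoint. That is too strong. It opens the second dosing phase, is the first-dose visit for Group 2 and, in Appendix 1, its dispensing visit, and it repeats the medication check and urine drug screen. It could also supply a covariate for the unspecified ANCOVA. Requiring it is a defensible per-protocol criterion. The narrower point remains: it contributes no primary measurement, and for Group 1, which takes no drug there, missing it leaves the clamp data and dosing intact.

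**The loss is soft.** Section 7.1 itself says that no formal power calculation was performed, the SD is carried over, and every miss rate above is assumed. A reader might infer that one exclusion takes the trial below 80%. That holds on n-2 df but not on 2n-3. At SD 1.2 power stays well above 80% after two exclusions (88.7% at 7/7, 87.9% at 6/8). At SD 1.6 it is below 80% with nobody lost.

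**Completion is undefined.** The both-groups figures require it to mean every listed item. On that reading a missed questionnaire on Day 1, 28 or 72 would exclude a subject too, so the issue is wider than Day 44.

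**Partial safeguards exist.** Visits can shift with the ±2-day clamp window (6.1), replacement is allowed (4.3), and spare drug is held for replacements (11.5). But replacement is discretionary and is described under withdrawal, which this subject does not meet on the clamp test.

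**Conclusion.** The point holds in conditional form. It is established that 7.2 and 4.3 use different completion tests, that 7.2 adds a visit with no primary measurement, and that 7.3 names no primary set. On the natural but unstated reading of 7.2, a subject with complete clamp data can be lost: mainly from Group 1 if the whole visit is missed, since Group 2 starts dosing there, and from either group if only part of the assessments is missing.

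Under the stated assumptions one such loss costs between 3 and 4 points of equivalence power at SD 1.4. The size depends on the carried-over SD, the true difference, the degrees of freedom and the absence of replacement. Its frequency cannot be estimated from the documents. This should be corrected because the rule costs precision and removing it is cheap, but it does not show that the trial will miss its power.

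**What to change.** - In 7.2, define the primary analysis set as all randomised subjects who complete the Day 1, 28 and 72 clamps. In 7.3, state that the primary model is fitted to that set.
- Remove Day 44 from primary evaluability. Keep it as a condition only for the secondary endpoints measured at that visit: lipids, adipocytokines, ghrelin, pituitary hormones, and the diet and sleep questionnaires.
- Report the primary model on the cohort as 7.2 now defines it, as a sensitivity analysis.
- Reconcile 4.3 with 7.2 so that one completion test applies to the primary endpoint.

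The change has one downside. A Group 2 subject who missed the Day 44 visit but had the third clamp could enter the primary set with shortened dolutegravir exposure. If the drug has an effect, that would pull the contrast towards zero and favour equivalence. Such subjects should be identified from the pill counts and accountability log (5.2, 11.5) and the recorded start and stop dates (9.2), and handled in the sensitivity analysis.

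The cost is a few sentences in 4.3, 7.2 and 7.3 and one extra model fit. No subjects, visits or assessments are added, and the primary set cannot be smaller than the present cohort.

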3.1 Endpoints

Primary Endpoint

- Change from baseline in total body glucose disposal by euglycaemic clamp method with 28 days dolutegravir treatment.

Secondary Endpoints

- Change from baseline in serum levels of fasting cholesterol and triglycerides
- Changes in adipocytokines, ghrelin and pituitary hormones
- Changes in indirect calorimetry
- Changes in food intake by food questionnaires
- Changes in sleep quality by sleep questionnaires
- Safety data including the number and severity of adverse events, as assessed by the medical dictionary for regulatory activities (MedDRA), from baseline to day 100

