5.2 Treatment Compliance

Adherence to investigational product will be evaluated using pill counts of returned / unused investigational product. This assessment will be documented in the drug accountability record.

6. Visit schedule & Procedures

The schedule of assessments is summarised in Appendix 1.

Screening Visit

The screening visit should take place within 28 days prior to study day 1.

Subjects will be provided with written information about the study in the form of a subject information sheet and will be allowed adequate time for questions and to consider the study before agreeing to participate. It will be the responsibility of the investigator or co-investigator to obtain written informed consent prior to undertaking any procedures detailed in the protocol.

The investigator or designee must provide adequate explanation of the aims, methods, objectives and potential hazards of the study. It must also be explained to the subject that they are free to refuse or withdraw from the study for any reason without detriment to their future care or treatment.

The following information and procedures will be recorded and performed as part of the screening assessments:

- Written Informed Consent
- Medical and medication history, including smoking and substance history
- Demographics; gender, ethnic origin, age, height, weight, and body mass index (BMI)
- Vital signs: temperature, blood pressure, heart rate, respiration rate, oxygen saturation
- Physical examination including measurement of waist and hip size

- Haematology complete blood count (FBC) with differential and platelet count (haemoglobin, haematocrit, erythrocyte count, white blood count, differential white blood cell count, platelets)
- Pregnancy testing and last menstrual period (LMP) date in WOCBP subjects
- Biochemistry safety labs assessment for standard clinical chemistry (glucose, creatinine, sodium, potassium, calcium, aspartate aminotransferase, alanine aminotransferase, bilirubin, CRP), including HbA1c
- HIV antibody testing, hepatitis C (antibody) and B (surface antigen) screening
- ECG
- Urinary analysis (pH, specific gravity, leucocytes, nitrite, protein, glucose, ketones, urobilinogen, bilirubin, erythrocytes) and urine drug screen

Baseline

Subjects who meet all the inclusion and exclusion criteria and wish to take part in the study will be admitted to the unit on the morning of day 1. Subjects will remain in the unit for approximately four to six hours.

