The following study assessments will be performed (subjects must have fasted for at least eight hours):

- Adverse events
- Concomitant medication
- Vital signs (during the clamp procedure vital signs will occur every 30 minutes)
- Height/ weight/ BMI
- Measurement of waist and hip size
- Haematology: complete blood count (FBC) with differential and platelet count (haemoglobin, haematocrit, erythrocyte count, white blood count, differential white blood cell count, platelets)
- Biochemistry safety labs assessment for standard clinical chemistry (fasting glucose, creatinine, sodium, potassium, calcium, aspartate aminotransferase, alanine aminotransferase, bilirubin), including thyroid hormones (TSH, ft4), lipids (triglycerides, cholesterol, cholesterol HDL & LDL Sub-fractions) CRP and Hb1aC
- Urinary analysis (pH, specific gravity, leucocytes, nitrite, protein, glucose, ketones, urobilinogen, bilirubin, erythrocytes) and urine drug screen
- Pregnancy testing and LMP date in WOCBP subjects
- Adiponectin, leptin, ghrelin, testosterone
- Pituitary hormone function tests

- Dietary Questionnaire
- Sleep Questionnaires (PSQI)
- Euglycaemic clamp 1
- Insulin will be titrated 3 times during euglycaemic clamp procedure according to approved and verified formula sheet.
- ECG monitoring at 30 minute intervals during the clamp procedure
- Indirect calorimetry (all participants)

Prior to baseline visit subjects will be randomly assigned to Group 1 or Group 2:

Group 1:

- Dolutegravir 50 mg once daily for the first 28 days of the study.
- No treatment for the last 44 days of the study.

Subject will be dispensed study medication (Dolutegravir 50 mg) and instructed to self-administer the study drugs at home from the morning of day 2 until the morning prior to the next euglycaemic clamp day (Day 27).

Group 2:

- No treatment for the first 43 days of the study.
- Dolutegravir 50 mg once daily for the last 28 days of the study (day 44-72).

Subject will be dispensed study medication (Dolutegravir 50 mg) and instructed to self-administer the study drugs at home from the morning of day 45 until the morning prior to the next euglycaemic clamp day (Day 71).

Day 28

Subjects will be admitted to the unit in the morning and remain on the unit for approximately four to six hours. Group 1 subjects will take their last dose of study medication in the unit in the morning of the visit.

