
 • Immediately discontinue DTG • Subject should not be rechallenged due to the risk of a recurrent reaction. • Report the event to Chelsea and Westminster NHS Trust R&D by telephone within 24 hours. • Events of possible drug-induced liver injury with hyperbilirubinemia² will be reported to Chelsea and Westminster NHS Trust R&D as serious adverse events using the serious adverse event case report form. • Complete the liver event case report form for all events meeting liver stopping criteria, and submit to Chelsea and Westminster NHS Trust R&D within one week of first becoming aware of the event • Perform liver event follow up assessments. • Monitor the subject until liver chemistries resolve, stabilise, or return to within baseline • Subject may continue in the study for any protocol specified follow up assessments. 
MONITORING:
 
 • Make every reasonable attempt to have subjects return to clinic within 24 hours for repeat liver chemistries (include ALT, AST, alkaline phosphatase, bilirubin) and perform liver event follow up assessments at the central laboratory as described to the right. • A specialist or hepatology consultation is recommended. • Monitor subjects twice weekly until liver chemistries resolve, stabilise or return to within baseline. 	
 • Viral hepatitis serology, including: 
 • Hepatitis A immunoglobulin M (IgM) antibody; • HBsAg and hepatitis B core antibody; • Hepatitis C RNA; • Hepatitis E IgM antibody. • Cytomegalovirus IgM antibody. • Epstein-Barr viral capsid antigen IgM antibody (or if unavailable, obtain heterophile antibody or monospot testing). • Syphilis screening. • Drugs of abuse screen, including alcohol. Record alcohol use on the liver event case report form • Serum acetaminophen adduct High Performance Liquid Chromatography assay (quantifies potential acetaminophen contribution to liver injury in subjects with definite or likely acetaminophen use in the preceding week [FDA, 2009]). The site must contact the medical monitor when this test is required. • Serum creatinine kinase and lactate dehydrogenase. • Fractionate bilirubin, if total bilirubin $\geq 1.5 \times \text{ULN}$. • Obtain complete blood count with differential to assess eosinophilia. • Anti-nuclear antibody, anti-smooth muscle antibody, Type 1 anti-liver kidney microsomal antibodies, and quantitative total immunoglobulin G (or gamma globulins). • Liver imaging (ultrasound, magnetic resonance, or computerised tomography) and /or liver biopsy to evaluate liver disease. Complete Liver

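### The evaluable cohort is set by attendance alone and the pill counts go unused, so poorly exposed subjects count as full dolutegravir clamps and can make equivalence easier to declare

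*Combined protocol and SAP*

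**What the plan says.** The primary endpoint in Section 3.1 is "Change from baseline in total body glucose disposal by euglycaemic clamp method with 28 days dolutegravir treatment". Section 1.2 explains the 28-day duration partly by the wish to reach steady state. The endpoint therefore presumes a course of drug, not a single dose.

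The cohort in Section 7.2 does not carry that presumption over: "All subjects who complete day 1, 28, 44 and 72 assessments (including all euglycaemic clamps) will form part of the evaluable cohort". Section 4.3 defines withdrawal in the same way: "A subject will be considered to have withdrawn from the study if they do not complete all euglycaemic clamp procedures". Neither passage mentions doses taken.

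On exposure, Section 5.2 says: "Adherence to investigational product will be evaluated using pill counts of returned / unused investigational product". The result goes into the drug accountability record. Section 7.3 gives the crossover model (treatment, period and sequence fixed, subject within sequence random) and the equivalence rule. It defines no per-protocol set, no adherence threshold and no adherence sensitivity analysis. Section 7.3 does not state outright that the primary model is run on the evaluable cohort, but no other set is defined for it.

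Dosing between visits takes place at home. Section 6 (Baseline) has Group 1 subjects "instructed to self-administer the study drugs at home from the morning of day 2", with a matching instruction for Group 2. One dose is observed on the clamp day: "Group 1 subjects will take their last dose of study medication in the unit in the morning of the visit" (Section 6, Day 28), and likewise for Group 2 on Day 72.

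**The concern.** In a superiority trial, counting non-adherent subjects as treated usually works against the claim. In an equivalence trial it can work for the claim. Section 7.3 declares equivalence when the 90% confidence interval for dolutegravir minus no treatment lies within ±1.1. A clamp recorded as dolutegravir in a subject who took little of the drug resembles a no-treatment clamp, so it moves the estimated difference toward zero and away from the margin.

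The trial has 16 subjects, so each one carries 1/16 (6.25%) of the estimate. If dolutegravir does alter insulin sensitivity, a few subjects who stopped or skipped home doses but kept their appointments could help produce a finding of no difference that 28 days of actual treatment would not support.

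**Working it through.** **Inputs.** SD of the difference 1.4 and margin ±1.1 (Section 7.1); 8 subjects per sequence, so n = 16 (Sections 4.1 and 7.1); 90% CI rule, which is two one-sided 5% tests (Section 7.3). Residual df = 16 − 2 = 14 for two sequences. Section 7.1 gives the SD for baseline versus week 4; I apply it to the dolutegravir minus no-treatment difference, which is an assumption.

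**Step 1: the plan's own figure.** SE = 1.4/√16 = 0.35, and t(0.95, 14 df) = 1.761. The CI half-width at the planned SD is 1.761 × 0.35 = 0.616, so the estimate must fall within ±(1.1 − 0.616) = ±0.484. Integrating over the sampling distribution of the SD, with a true difference of 0, gives 82.0% power at n = 16 and 78.3% at n = 15. Sixteen is thus the smallest total that reaches the stated 80%, and the plan's sample size is reproduced.

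**Step 2: add k unexposed subjects.** Let the true effect be Δ in exposed subjects and 0 in unexposed subjects.

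- Mean of the estimate: Δ × (16 − k)/16.
- The mixture also inflates the observed SD. With k₁ and k₂ unexposed subjects in the two sequences, the expected pooled variance is 1.4² + Δ² × [k₁(8 − k₁)/8 + k₂(8 − k₂)/8]/14.

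For Δ = 1.1 and k = 1: mean 1.1 × 15/16 = 1.03; variance 1.96 + 1.21 × 0.875/14 = 2.036, SD 1.43. For k = 2 (one per sequence): mean 0.96; variance 1.96 + 1.21 × 1.75/14 = 2.111, SD 1.45. For k = 4 (two per sequence): mean 0.825; variance 1.96 + 1.21 × 3/14 = 2.219, SD 1.49.

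**Step 3: probability that the 90% CI lies within ±1.1.** The estimate is normal with the mean above and SE 0.35. The residual sum of squares divided by 1.96 is non-central chi-square on 14 df, with non-centrality Δ² × [bracket above]/1.96. Unexposed subjects are spread evenly over the sequences.

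| Unexposed of 16 | True effect 0 | 0.55 | 1.1 (margin) | 1.5 |
|---|---|---|---|---|
| 0 | 82% | 44% | 5.0% | 0.3% |
| 1 | 82% | 47% | 6.9% | 0.6% |
| 2 | 82% | 50% | 9.2% | 1.0% |
| 4 | 82% | 57% | 15.9% | 3.0% |

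At 1.1 and 1.5 a declaration of equivalence is an error; at 0 and 0.55 it is correct. If the unexposed all fall in one sequence, the margin column reads 9.3% for two and 16.7% for four. Holding the SD at 1.4 would give 7.2%, 10.2% and 18.5% for 1, 2 and 4, but that ignores the variance that the mixture adds.

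**Step 4: cost of leaving such subjects out.** With no replacement and a true difference of 0, power is 82.0% at n = 16, 78.3% at n = 15 (13 df) and 73.9% at n = 14 (12 df).

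**The case against.** The protocol has some controls. Adherence is measured. Section 4.3 says "The investigator also has the right to withdraw subjects from the study in the event of intercurrent illness, adverse events, protocol violations", and it also allows replacement. A dose is taken in the unit on the clamp morning, and Section 11.5 provides spare drug for anyone who forgets theirs. A subject who skipped home doses is therefore not drug-free at the clamp, and zero effect is the extreme case. These points reduce the problem without removing it. Withdrawal for violations is discretionary and has no adherence threshold, and one observed dose does not supply the 28 days named in the endpoint.

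A reader might go further and infer that a subject taken off dolutegravir early for a liver event would stay in and be counted as treated, because Appendix 5 says: "Subject may continue in the study for any protocol specified follow up assessments". The documents do not support building on that. Section 7.5 directs that subjects whose drug is stopped for liver reasons leave the study, and Appendix 5 speaks of follow-up, not clearly of later clamps. Appendix 1 schedules biochemistry at screening, baseline and Days 28, 44 and 72, so the first scheduled liver test on drug falls on the clamp day in both groups. What does stand is that Section 7.5 and Appendix 5 conflict and must be reconciled. Sections 7.5 and 7.6 also withdraw subjects for allergy, rash, suicidality and pregnancy, so the gap mainly concerns missed or self-stopped home doses.

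A reader might also infer that the trial is biased toward equivalence as designed. That is too strong: there is no bias if dolutegravir has no effect or if everyone takes it, and the documents give no adherence rate.

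Finally, excluding subjects on adherence selects them after randomisation and costs power. Both are true, and they are reasons not to rely on an exposed set alone.

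**Conclusion.** The point holds as a conditional one. The plan admits subjects to its only non-safety cohort on attendance and never uses the exposure data it collects. If dolutegravir has a non-zero effect and some completers were largely off drug, the false-equivalence rate exceeds the nominal 5%: about 6.9%, 9.2% and 16% for 1, 2 and 4 wholly unexposed subjects when the true effect equals the margin. Two such subjects nearly double the error rate.

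These figures rest on the plan's SD of 1.4, 16 analysed subjects, 14 df, an assumed number of unexposed subjects and zero effect in each of them. Partial exposure would give smaller increases. The matter should be corrected before analysis, but it does not by itself invalidate the design.

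**What to change.** In Sections 7.2 and 7.3, pre-specify an exposure-based (per-protocol) set: evaluable subjects whose pill count for the dolutegravir phase shows at least a stated share of scheduled doses. The sponsor should fix that share before analysis. Run the same crossover model in this set and in all completers, and claim equivalence only if the 90% CI rule is met in both. State explicitly that these are the sets for the primary model. Separately, reconcile Section 7.5 with Appendix 5 on whether a subject remains in the study after a liver stop, and say how any clamp data from such a subject are handled.

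The change needs no new data, since Appendix 1 already has drug returns at Day 28 (Group 1) and Day 72 (Group 2), and only one further run of the model. The real cost is power. Requiring both sets to agree cannot give more power than the exposed set alone, which has about 82% with 16 subjects, 78% with 15 and 74% with 14 if those who leave are not replaced. One unreplaced loss thus drops below the 80% target. The exposed set is also selected after randomisation, which is why the all-completers analysis should be kept beside it.
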